14.4.2.1.6	Scatter Plot: CTrough vs. Change from Baseline in CSF Biomarker (pTau/A $\beta$ 1-42 Ratio) Efficacy Population	IP	14.4.2.1.1
14.4.2.1.7	Scatter Plot: CTrough vs. Change from Baseline in CSF Biomarker (Brain derived neurotrophic factor (BDNF)) Efficacy Population	IP	14.4.2.1.1
14.4.2.2.1	Scatter Plot: CTrough vs. Combined Change from Baseline in Z-score of Total Recall and Delayed Recall on the HVL T-R Efficacy Population	IP	14.4.2.1.1
14.4.2.2.2	Scatter Plot: CTrough vs. Change from Baseline in Wechsler Memory Scale (WMS) Immediate and Delayed Recall Composite Score Efficacy Population	IP	14.4.2.1.1
14.4.2.2.3	Scatter Plot: CTrough vs. Change from Baseline in Clinical Dementia Rating Scale-Sum of Boxes (CDR-SB) Efficacy Population	IP	14.4.2.1.1
14.4.2.2.4	Scatter Plot: CTrough vs. Change from Baseline in Mini-Mental State Examination (MMSE) Score Efficacy Population	IP	14.4.2.1.1
14.4.3.1.1	Scatter Plot: Cmax vs. Change from Baseline in CSF Biomarker (T-tau) Efficacy Population	IP	14.4.2.1.1
14.4.3.1.2	Scatter Plot: Cmax vs. Change from Baseline in CSF Biomarker (P-tau181) Efficacy Population	IP	14.4.2.1.1
14.4.3.1.3	Scatter Plot: Cmas vs. Change from Baseline in CSF Biomarker (A $\beta$ 1-40) Efficacy Population	IP	14.4.2.1.1
14.4.3.1.4	Scatter Plot: Cmax vs. Change from Baseline in CSF Biomarker (A $\beta$ 1-42) Efficacy Population	IP	14.4.2.1.1
14.4.3.1.5	Scatter Plot: Cmax vs. Change from Baseline in CSF Biomarker (Neurofilament light chain) Efficacy Population	IP	14.4.2.1.1
14.4.3.1.6	Scatter Plot: Cmax vs. Change from Baseline in CSF Biomarker (pTau/A $\beta$ 1-42 Ratio) Efficacy Population	IP	14.4.2.1.1
14.4.3.1.7	Scatter Plot: Cmax vs. Change from Baseline in CSF Biomarker (Brain derived neurotrophic factor (BDNF)) Efficacy Population	IP	14.4.2.1.1

14.4.3.2.1	Scatter Plot: Cmax vs. Combined Change from Baseline in Z-score of Total Recall and Delayed Recall on the HVLt-R Efficacy Population	IP	14.4.2.1.1
14.4.3.2.2	Scatter Plot: Cmax vs. Change from Baseline in Wechsler Memory Scale (WMS) Immediate and Delayed Recall Composite Score Efficacy Population	IP	14.4.2.1.1
14.4.3.2.3	Scatter Plot: Cmax vs. Change from Baseline in Clinical Dementia Rating Scale-Sum of Boxes (CDR-SB) Efficacy Population	IP	14.4.2.1.1
14.4.3.2.4	Scatter Plot: Cmax vs. Change from Baseline in Mini-Mental State Examination (MMSE) Score Efficacy Population	IP	14.4.2.1.1

Listing Number	Listing Title	Validation Method	Shell Number (if repeat)
16.2	Subject Data Listings		
16.2.1	Discontinued Subjects		
16.2.1.1	Subject Disposition (Enrolled Subjects)	IP	
16.2.1.2	Screen Failures	IP	
16.2.1.3	Early Withdrawals (Enrolled Subjects)	IP	
16.2.2	Protocol Deviations		
16.2.2.1	Protocol Deviations (Protocol Deviations)	IP	
16.2.3	Subjects Excluded From The Efficacy Analyses		
16.2.3.1	Analysis Sets (Enrolled Subjects)	IP	
16.2.4	Demographic Data, Medical History and Medications		
16.2.4.1	Subject Randomization (Randomized Subjects)	IP	
16.2.4.2	Demographic Data (Enrolled Subjects)	IP	
16.2.4.3	Computed tomography (CT)/Magnetic Resonance Imaging (MRI) Data (Enrolled Subjects)	IP	
16.2.4.4.1	Prior Medical History (Enrolled Subjects)	IP	
16.2.4.4.2	Ongoing Medical History (Enrolled Subjects)	IP	

Listing Number	Listing Title	Validation Method	Shell Number (if repeat)
16.2.4.4.3	Medical History-Probable Alzheimer's Diagnosis (Enrolled Subjects)	IP	
16.2.4.5.1	Inclusion Criteria Not Met (Enrolled Subjects)	IP	
16.2.4.5.2	Exclusion Criteria Met (Enrolled Subjects)	IP	
16.2.4.6.1	Prior and Concomitant Medications (Enrolled Subjects)	IP	
16.2.4.6.2	Prior and Concomitant Alzheimer's Medications (Enrolled Subjects)	IP	
16.2.5	Compliance And/Or Drug Concentration Data	IP	
16.2.5.1	Study Drug Exposure and Compliance (Enrolled Subjects)	IP	
16.2.5.2	Plasma Pharmacokinetic Parameters of Neflamapimod Concentrations Over Time (Enrolled Subjects)	IP	
16.2.5.3	Individual Pharmacokinetic Parameters of Neflamapimod (Enrolled Subjects)	IP	
16.2.6	Individual Efficacy Response Data and PD data		
16.2.6.1.1	Hopkins Verbal Learning Test – Revised (HVLT-R) (Enrolled Subjects)	IP	
16.2.6.1.2	Combined Change from Baseline in Z-score of Total Recall and Delayed Recall on the HVLT-R (Enrolled Subjects)	IP	
16.2.6.2	Wechsler Memory Scale (WMS) (Enrolled Subjects)	IP	
16.2.6.3	Clinical Dementia Rating (CDR) (Enrolled Subjects)	IP	
16.2.6.4	Mini-Mental State Examination (MMSE) (Enrolled Subjects)	IP	
16.2.6.5	Cerebrospinal Fluid (CSF) Biomarkers (Enrolled Subjects)	IP	
16.2.7	Adverse Event Listings	IP	
16.2.7.1	Adverse Events (Enrolled Subjects)	IP	
16.2.7.2	All Serious Adverse Events (Enrolled Subjects)	IP	
16.2.8	Individual Laboratory Measurements And Other Safety and PD data		
16.2.8.1.1	Hematology Results (Enrolled Subjects)	IP	

Listing Number	Listing Title	Validation Method	Shell Number (if repeat)
16.2.8.1.2	Chemistry Results (Enrolled Subjects)	IP	
16.2.8.1.3	Coagulation Results (Enrolled Subjects)	IP	
16.2.8.1.4	Clinically Significant Laboratory Results (Enrolled Subjects)	IP	
16.2.8.1.5	Laboratory Liver Function and Coagulation Parameter Abnormalities (Enrolled Subjects)	IP	
16.2.8.2	Vital Signs (Enrolled Subjects)	IP	
16.2.8.3	12-lead ECG Parameters (Enrolled Subjects)	IP	
16.2.8.4	Physical Examination, Abnormal Results (Enrolled Subjects)	IP	
16.2.8.5	Columbia Suicide Severity Rating Scale (C-SSRS) Questionnaire (Enrolled Subjects)	IP	

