### 4 SAMPLE SIZE

Up to 76 subjects per treatment arm (152 total) provides 90% power to detect ES of 0.53 and 80% power to detect ES of 0.46. This level of ES is the minimum treatment effect amount considered clinically relevant and is less than the effect size seen in the Phase 2a studies.

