## 6.10 Efficacy Analyses

All efficacy analyses will be based on the Evaluable Efficacy Population by randomized treatment regardless of the treatment actually received. Descriptive statistics by treatment group

and visit will be reported for all efficacy endpoints. All statistical tests will be performed using a two-tailed 5% overall significance level, unless otherwise stated. All comparisons between treatments will be reported with 95% confidence intervals for the difference.

There will be no imputation of missing efficacy data.

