### 6.10.2 Primary Efficacy Analysis

The primary endpoint will be analyzed using Mixed Model for Repeated Measures (MMRM) with fixed effects for treatment, background AD-specific therapy (cholinesterase inhibitor or memantine versus no cholinesterase inhibitor or memantine), CDR-Global Score of 0.5 versus 1.0, scheduled visit (nominal) and scheduled visit by treatment interaction, random effect for subject and baseline z-score as a covariate. Least-square means (LSM) and 2-sided 95% confidence intervals (CI) will be provided for treatment group differences and estimated endpoint values by visit.

The normally-distributed assumption for the combined change in z-scores of total recall and delayed recall on the HVLT-R will be examined (at 0.05 alpha level). In case the assumption is violated, rank transformed data will be applied to the MMRM model. Ranks will be determined separately within each time point, based on observed data only.

In addition, Scale plot will be provided for combined change in z-scores of total recall and delayed recall on the HVLT-R at each post-baseline visit by treatment group.

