#### 6.10.5 Exploratory Analyses

Additional exploratory analyses may be performed to further study the effects of treatment as data warranted. Numerical exploratory endpoints will be analyzed using analysis of covariance, t-tests, or Wilcoxon sign rank test. Analysis of categorical exploratory endpoints will be performed using chi-square test. Exploratory endpoints include

- Change of total recall on the HVLt-R
- Change of delayed recall on the HVLt-R
- Change of retention (%) on the HVLt-R
- Change of recognition on the HVLt-R
- Change of recognition on the WMS
- Subgroups analyses by , sex (male/female), age (dichotomized at pretreatment median age), race (white vs. non-white, Hispanic vs. non-Hispanic), CYP2C19 genotype status and/or other grouping covariates, if data permit.
- Outlier analyses to identify the impact of any extreme values on the analysis results.
- Categorical exploratory endpoints (i.e. responder analysis), if data permit, will be performed using Pearson's chi-square test

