14.2.3.3	Mixed Models for Repeated Measures Analysis of Combined Change from Baseline in Z-score of Total Recall and Delayed Recall on the Hopkins Verbal Learning Test – Revised (HVLTR) Per-Protocol Population	Stat IP	14.2.1.3
14.2.3.4	Analysis of Covariance of Combined Change from Baseline in Z-score of Total Recall and Delayed Recall on the Hopkins Verbal Learning Test – Revised (HVLTR) Efficacy Population	Stat IP	
14.2.3.5	Analysis of Covariance of Combined Change from Baseline in Z-score of Total Recall and Delayed Recall on the Hopkins Verbal Learning Test – Revised (HVLTR) Per-Protocol Population	Stat IP	
14.2.4	Exploratory Endpoints		
14.2.4.1	Analysis of Covariance of Change from Baseline in Total Recall on the Hopkins Verbal Learning Test – Revised (HVLTR) Efficacy Population	IP	
14.2.4.2	Analysis of Covariance of Change from Baseline in Delayed Recall on the Hopkins Verbal Learning Test – Revised (HVLTR) Efficacy Population	IP	14.2.4.1
14.2.4.3	Analysis of Covariance of Change from Baseline in Retention (%) on the Hopkins Verbal Learning Test – Revised (HVLTR) Efficacy Population	IP	14.2.4.1
14.2.4.4	Analysis of Covariance of Change from Baseline in Recognition on the Hopkins Verbal Learning Test – Revised (HVLTR) Efficacy Population	IP	14.2.4.1
14.2.4.5	Analysis of Covariance of Change from Baseline in Wechsler Memory Scale (WMS) Recognition Composite Tests of Logical Memory II, Verbal Paired Associates II and Visual Reproduction II (0-60) Efficacy Population	IP	14.2.4.1

14.2.4.6.x	Subgroup Analysis of Covariance of Combined Change from Baseline in Z-score of Total Recall and Delayed Recall on the HVLTL-R Efficacy Population	IP	
14.2.4.7	Pearson's Chi-square Test for Responder Efficacy Population	IP	
14.2.5-14.2.6	Subgroup Analyses		
14.2.5.1.1	Hopkins Verbal Learning Test – Revised (HVLTL-R), Cholinesterase Inhibitor or Memantine Efficacy Population	IP	
14.2.5.1.2	Hopkins Verbal Learning Test – Revised (HVLTL-R), No Cholinesterase Inhibitor or Memantine Efficacy Population	IP	
14.2.5.2.1	Combined Change from Baseline in Z-score of Total Recall and Delayed Recall on the Hopkins Verbal Learning Test – Revised (HVLTL-R), Cholinesterase Inhibitor or Memantine Efficacy Population	IP	
14.2.5.2.2	Combined Change from Baseline in Z-score of Total Recall and Delayed Recall on the Hopkins Verbal Learning Test – Revised (HVLTL-R), No Cholinesterase Inhibitor or Memantine Efficacy Population	IP	

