14.2.5.3	Mixed Models for Repeated Measures Analysis of Combined Change from Baseline in Z-score of Total Recall and Delayed Recall on the Hopkins Verbal Learning Test – Revised (HVLTL-R) by Background AD-specific Therapy Efficacy Population	IP	
14.2.6.1.1	Wechsler Memory Scale (WMS) Subscore, Cholinesterase Inhibitor or Memantine Efficacy Population	IP	
14.2.6.1.2	Wechsler Memory Scale (WMS) Subscore, No Cholinesterase Inhibitor or Memantine Efficacy Population	IP	

14.2.6.2.1	Wechsler Memory Scale (WMS) Composite and Overall Score, Cholinesterase Inhibitor or Memantine Efficacy Population	IP	
14.2.6.2.2	Wechsler Memory Scale (WMS) Composite and Overall Score, No Cholinesterase Inhibitor or Memantine Efficacy Population	IP	
14.2.6.3	Mixed Models for Repeated Measures Analysis of Change from Baseline in Wechsler Memory Scale (WMS) Immediate and Delayed Recall Composite Score (0-228) by Background AD-specific Therapy Efficacy Population	IP	14.2.5.3
14.2.6.4.1	Clinical Dementia Rating (CDR), Cholinesterase Inhibitor or Memantine Efficacy Population	IP	
14.2.6.4.2	Clinical Dementia Rating (CDR), No Cholinesterase Inhibitor or Memantine Efficacy Population	IP	
14.2.6.5	Mixed Models for Repeated Measures Analysis of Change from Baseline in Clinical Dementia Rating Scale-Sum of Boxes (CDR-SB) by Background AD-specific Therapy Efficacy Population	IP	14.2.5.3
14.2.6.6.1	Mini-Mental State Examination (MMSE), Cholinesterase Inhibitor or Memantine Efficacy Population	IP	
14.2.6.6.2	Mini-Mental State Examination (MMSE), No Cholinesterase Inhibitor or Memantine Efficacy Population	IP	
14.2.6.7	Analysis of Covariance of Change from Baseline in Mini-Mental State Examination (MMSE) Score by Background AD-specific Therapy Efficacy Population	IP	
14.2.6.8.1	CSF Biomarkers (T-tau, P-tau181, A $\beta$ 1-40, A $\beta$ 1-42, Neurogranin, Neurofilament Light Chain, pTau/A $\beta$ 1-42 Ratio), Cholinesterase Inhibitor or Memantine Efficacy Population	IP	
14.2.6.8.1	CSF Biomarkers (T-tau, P-tau181, A $\beta$ 1-40, A $\beta$ 1-42, Neurogranin, Neurofilament Light Chain,	IP	

	pTau/A $\beta$ 1-42 Ratio), No Cholinesterase Inhibitor or Memantine Efficacy Population		
14.2.6.9.1	Analysis of Covariance of Change from Baseline in CSF Biomarker (T-tau) by Background AD-specific Therapy Efficacy Population	IP	14.2.6.7
14.2.6.9.2	Analysis of Covariance of Change from Baseline in CSF Biomarker (P-tau181) by Background AD-specific Therapy Efficacy Population	IP	14.2.6.7

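### HVLT-R total recall and delayed recall, the two halves of the primary composite, are planned as ANCOVA although the composite gets an MMRM, so they do not add up to the primary estimate

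*SAP*

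**What the plan says.** - **Composite.** SAP 6.2.12 defines Z as half the total recall z-score plus half the delayed recall z-score, both scaled on the baseline mean and SD. SAP 6.10.2 analyses its change by MMRM with visit and visit-by-treatment terms. Table 14.2.1.3 is titled "Mixed Models for Repeated Measures Analysis of Combined Change from Baseline in Z-score of Total Recall and Delayed Recall".
- **The two halves.** SAP 6.10.5 lists change in total recall and in delayed recall as exploratory: "Numerical exploratory endpoints will be analyzed using analysis of covariance, t-tests", with a Wilcoxon test as the third option. MMRM is not offered. Table 14.2.4.1 is "Analysis of Covariance of Change from Baseline in Total Recall on the Hopkins Verbal Learning Test", and Table 14.2.4.2 does the same for delayed recall.
- **Subgroups of the composite.** Table 14.2.4.6.x, which serves the exploratory subgroups of 6.10.5 (sex, age, race or ethnicity, CYP2C19), is "Subgroup Analysis of Covariance of Combined Change from Baseline in Z-score of Total Recall and Delayed Recall". The background-therapy, weight and CDR subgroups get MMRM (Tables 14.2.5.3, 14.2.6.10.5, 14.2.6.14.5).
- **WMS.** The immediate and delayed halves each have an MMRM table (14.2.2.3.1, 14.2.2.3.2).
- **Missing data.** SAP 6.10: "There will be no imputation of missing efficacy data". SAP 6.2.16 assigns early termination (ET) efficacy data to the next scheduled visit.
- **Visits.** HVLT-R is given at baseline, Days 42, 84 and 168, and at the ET visit (Protocol Table 6-1).

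**The concern.** The primary objective names both immediate and delayed recall. Whatever the primary result, readers will next ask which half carries it. As planned, the answer comes from a different model, a different set of subjects and a different missing-data assumption from the primary estimate, so a difference between model and model is mixed with a difference between component and component. ANCOVA suits the CSF markers, which have one post-baseline sample, but HVLT-R has three post-baseline visits. The plan gives no reason for treating the HVLT-R halves differently from the WMS halves, or for modelling the same composite two ways across subgroups.

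**Working it through.** **1. The plan's own figure.** SAP 4 says that 76 per arm "provides 90% power to detect ES of 0.53 and 80% power to detect ES of 0.46". With two-sided alpha 0.05 (SAP 6.10), power = Φ(ES·√(n/2) − 1.96), and √38 = 6.164.
- ES 0.53: 3.267 − 1.960 = 1.307, power 90.4%.
- ES 0.46: 2.836 − 1.960 = 0.876, power 80.9%.

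The noncentral t (150 df) gives 90.1% and 80.4%. The figures reproduce. I use 0.46 as the true effect below.

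**2. When the halves add up.** The baseline SDs s_T and s_D are fixed, so ΔZ = 0.5·ΔT/s_T + 0.5·ΔD/s_D. If both halves and the composite have the same linear model, subjects and covariates, then 0.5·b_T/s_T + 0.5·b_D/s_D equals the composite effect exactly.
- ANCOVA halves against the ANCOVA composite: gap below 1e-15 with shared covariates. With each half's own baseline, the gap SD is 0.003 to 0.004.
- ANCOVA halves against the MMRM composite: no such identity. The MMRM also uses Days 42 and 84 and the subjects without a Week 24 value. In addition, 6.10.2 states one baseline slope for all visits, whereas a Week 24 ANCOVA fits its own. So part of the gap is model form and would remain without dropout.

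**3. Size of the gap.** 500 simulated trials of 152 subjects per setting. Assumptions not in the documents: correlation 0.75 between total and delayed recall, about 0.59 from baseline to Week 24, the dropout rates and mechanisms, an unstructured covariance, and strata omitted. Entries are mean / SD, in z.

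| Dropout | ANCOVA halves − MMRM composite, random | Same, placebo-only dependence on decline | MMRM halves − MMRM composite, SD |
|---|---|---|---|
| 5% | 0.000 / 0.032 | −0.015 / 0.029 | 0.002 |
| 10% | 0.003 / 0.031 | −0.024 / 0.035 | 0.002 |
| 15% | −0.002 / 0.040 | −0.037 / 0.038 | 0.002 to 0.003 |
| 25% | 0.000 / 0.048 | −0.062 / 0.054 | 0.003 to 0.004 |

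**4. Bias at Week 24.** Large-sample simulation (100,000 subjects per setting), composite scale, dropout depending on the last observed change, Monte Carlo error about 0.005. The first four result columns are ANCOVA on subjects with a Week 24 value.

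| Dropout | Random | Decline, both arms alike | Decline, placebo only | Opposite by arm | Unstructured MMRM, placebo only |
|---|---|---|---|---|---|
| 5% | −0.006 | −0.001 | −0.012 | −0.036 | 0.000 |
| 10% | −0.004 | 0.001 | −0.027 | −0.062 | −0.002 |
| 15% | 0.004 | −0.005 | −0.046 | −0.088 | −0.010 |
| 25% | −0.007 | −0.008 | −0.072 | −0.150 | −0.008 |

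Total recall alone is nearly the same (placebo only: −0.014, −0.029, −0.045, −0.070). SAP 6.10.2 names a random subject effect and no covariance structure. With compound symmetry the placebo-only MMRM bias is −0.003, −0.008, −0.020 and −0.024, still smaller than for ANCOVA.

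A second simulation (4,000 trials per setting, correlation 0.65 between occasions and 0.7 between components, placebo decliners likelier to leave) agrees. At 10, 15 and 20% dropout, component ANCOVA averaged 0.433, 0.421 and 0.413 against 0.458, 0.457 and 0.461 for MMRM. The ANCOVA bias is 0.433 − 0.46 = −0.027, then −0.039 and −0.047. Under random dropout it showed no bias, and an MMRM variance 2 to 4% lower.

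**5. The ET rule.** If every dropout has an ET score moved to the next HVLT-R visit, the placebo-only ANCOVA bias becomes −0.002, −0.006, −0.014 and −0.024 at 5, 10, 15 and 25% dropout.

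**6. Scale.** The sampling SD of the Week 24 effect is about 0.13. A bias of 0.012 to 0.046 is 0.012/0.13 = 0.09 to 0.046/0.13 = 0.35 of that SD.

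**The case against.** The strongest reply is that a bridge is already planned. SAP 6.10.3 and Table 14.2.3.4 analyse the composite itself by ANCOVA at Week 24, and by step 2 the ANCOVA halves sum to that result almost exactly. Figures 14.2.1.2 and 14.2.1.3 also show each half by visit and arm. This stands, but the bridge leads to a sensitivity analysis and not to the primary estimate.

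A reader might infer that the exploratory subgroup effects cannot be compared with the overall effect. The documents do not support that: ANCOVA subgroups compare directly with the ANCOVA composite in Table 14.2.3.4. They are only not like-for-like with the MMRM subgroup tables. A simpler model is also defensible for small race or genotype cells.

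A reader might also infer that ANCOVA is biased whenever dropout depends on earlier scores. It is not. The dependence must differ between arms, and nothing in the documents says that it will.

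Three further points stand. SAP 6.10.5 makes these analyses optional, and 6.10.7 treats supportive analyses as descriptive. Retention and recognition are not parts of the composite, so the adding-up argument does not reach them. And if the normality check in 6.10.2 sends the composite to ranks, additivity is lost under any model.

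**Conclusion.** The point holds as a consistency weakness in exploratory analyses. The ANCOVA halves miss the primary MMRM estimate by an SD of about 0.03 to 0.05 z even with random dropout, against 0.002 to 0.004 with MMRM halves. Bias is conditional: roughly 0.01 to 0.05 SD toward no effect at 5 to 15% dropout if decline drives dropout in the placebo arm only, about zero if dropout is random or follows decline equally in both arms, and smaller where ET scores reach Week 24.

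These sizes rest on the assumed correlations and dropout. The documents give no dropout rate; they say only that withdrawals before Day 21 are replaced (Protocol 4.3, 6.2.12). That the ANCOVA is an observed-value analysis at Week 24 is itself inferred: neither SAP 6.10.5 nor the table titles state the visit. The ET rule is also not fully clear, because Day 126 is a scheduled visit without HVLT-R.

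A reader might conclude that the primary result is compromised. It is not: the primary test, its alpha and the sample size do not depend on these tables.

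**What to change.** - In SAP 6.10.5 and Tables 14.2.4.1 and 14.2.4.2, analyse change in total recall and in delayed recall with the 6.10.2 MMRM, each with its own baseline as covariate, and report the Week 24 contrast. Shell 14.2.1.3 can be reused, as it already is for WMS.
- Keep the ANCOVA as a supportive line and state its visit.
- In Table 14.2.4.6.x, use the same MMRM where cell sizes permit, so that these subgroups match Tables 14.2.5.3, 14.2.6.10.5 and 14.2.6.14.5.
- Changing retention and recognition is optional.

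The cost is SAP wording, table titles and minor extra programming. No new data or subjects are needed.

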6.2.5. Genotyping and Apolipoprotein E4 Testing

A blood sample will be collected from all subjects at Visit 3 (Day 1) for CYP2C19 genotyping; such testing is mandatory. The CYP2C19 gene encodes for a drug metabolizing enzyme that accounts for approximately half the metabolism of neflamapimod. (The other is the CYP3A4 enzyme). As there are known polymorphisms in CYP2C19, particularly in Asian populations, that reduce the function of this enzyme, the PK profiles in individual subjects may be impacted CYP2C19 genotype (Fricke-Galindo et al, 2016). PK profiles will be obtained in all subjects and correlated against CYP2C19 genotype (see Section 6.2.8 and Section 8.4). An aliquot of blood from this sample may also be used for measurement of apolipoprotein E4; such testing is optional. Results will be available to study sites and may be discussed with the subjects only after the clinical study report has been completed.

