#### **6.1.2 Evaluable Efficacy Population**

The Efficacy Population used for efficacy analyses, consistent with the intent-to-treat (ITT) principles includes all subjects who received at least one dose of study drug and had at least one post-dose efficacy assessment.

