#### **6.1.4 Pharmacokinetics (PK) Population**

The Pharmacokinetics (PK) Population includes all randomized subjects who received at least one dose of study drug in neflamapimod treatment group and had at least one post-dose PK data assessment.

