### **6.2.9 Inexact Values**

In the case where a variable is recorded as “> x”, “≥ x”, “< x” or “≤ x”, a value of x will be taken for analysis purposes, Where a range of values is quoted the midpoint of the range will be taken.

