14.3.5.1	Study Drug Exposure and Compliance Safety Population	IP	
14.3.6	Vital Signs And Physical Examination		
14.3.6.1	Vital Signs Safety Population	IP	

14.3.6.2	Physical Examinations at Post-baseline Visits Safety Population	IP	
14.3.6.3	Body Weight Safety Population	IP	
14.3.7	Other Safety		
14.3.7.1	12-lead ECG Safety Population	IP	
14.3.7.2	12-lead ECG Result Interpretations Safety Population	IP	
14.3.7.3	12-lead ECG Abnormalities for Subjects with Any Abnormal Clinically Significant ECG Interpretation Safety Population	IP	
14.3.7.4	12-lead ECG – QT, QTc, and QTcF Categories QTcF Categories Safety Population	IP	
14.3.8	Concomitant Medication		
14.3.8.1	Concomitant Medications Safety Population	IP	
14.4	PK Data		
14.4.1.1	Neflamapimod Concentrations by Visit PK Population	IP	
14.4.1.2	Pharmacokinetic Parameters of Neflamapimod PK Population	IP	
14.4.1.3.x	Pharmacokinetic Parameters of Neflamapimod by CYP2C19 Genotype Status PK Population	IP	
14.4.2	Correlation Analysis of PK Parameters and Efficacy Data (Combined Change in Z-score, Change in WMS, CDR-SB) Efficacy Population	IP	
14.4.3	Correlation Analysis of PK Parameters and Change from Baseline in CSF Biomarkers Efficacy Population	IP	

Figure Number	Figure Title	Validation Method	Shell Number (If Repeat)
14.2 Figure	Figure for Efficacy Data		
14.2.1.1	Mean ( $\pm$ SE) Combined Change from Baseline in Z-score of Total Recall and Delayed Recall on the HVLTR by Visit and by Treatment Efficacy Population	IP	

14.2.1.2	Mean ( $\pm$ SE) Change from Baseline in Total Recall on the HVLТ-R by Visit and by Treatment Efficacy Population	IP	14.2.1.1
14.2.1.3	Mean ( $\pm$ SE) Change from Baseline in Delayed Recall on the HVLТ-R by Visit and by Treatment Efficacy Population	IP	14.2.1.1
14.2.2	Mean ( $\pm$ SE) Change from Baseline in Wechsler Memory Scale (WMS) Immediate and Delayed Recall Composite Score by Visit and by Treatment Efficacy Population	IP	14.2.1.1
14.2.3	Mean ( $\pm$ SE) Change from Baseline Clinical Dementia Rating Scale-Sum of Boxes (CDR-SB) by Visit and by Treatment Efficacy Population	IP	14.2.1.1
14.2.4	Mean ( $\pm$ SE) Change from Baseline in Mini-Mental State Examination (MMSE) Score by Visit and by Treatment Efficacy Population	IP	14.2.1.1
14.2.5.1	Box Plot of CSF Biomarker (T-tau) Efficacy Population	IP	
14.2.5.2	Box Plot of CSF Biomarker (P-tau181) Efficacy Population	IP	14.2.5.1

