14.2.5.3	Box Plot of CSF Biomarker (A $\beta$ 1-40) Efficacy Population	IP	14.2.5.1
14.2.5.4	Box Plot of CSF Biomarker (A $\beta$ 1-42) Efficacy Population	IP	14.2.5.1
14.2.5.5	Box Plot of CSF Biomarker (Neurofilament Light Chain) Efficacy Population	IP	14.2.5.1
14.2.5.6	Box Plot of CSF Biomarker (pTau/A $\beta$ 1-42 Ratio) Efficacy Population	IP	14.2.5.1
14.2.5.7	Box Plot of CSF Biomarker (Brain derived neurotrophic factor (BDNF)) Efficacy Population	IP	
14.3 Figure	Figure for Safety Data		
14.3.1.1	Box Plot of Change from Baseline in Heart Rate (beats/min) Safety Population	IP	
14.3.1.2	Box Plot of Change from Baseline in PR (msec) Safety Population	IP	14.3.1.1

14.3.1.3	Box Plot of Change from Baseline in RR (msec) Safety Population	IP	14.3.1.1
14.3.1.4	Box Plot of Change from Baseline in QT (msec) Safety Population	IP	14.3.1.1
14.3.1.5	Box Plot of Change from Baseline in QRS (msec) Safety Population	IP	14.3.1.1
14.3.1.6	Box Plot of Change from Baseline in QTcF (msec) Safety Population	IP	14.3.1.1
14.3.1.7	Box Plot of Change from Baseline in QTc (msec) Safety Population	IP	14.3.1.1
14.3.2.1	Box Plot of Change from Baseline in Systolic Blood Pressure (mmHg) Safety Population	IP	
14.3.2.2	Box Plot of Change from Baseline in Diastolic Blood Pressure (mmHg) Safety Population	IP	14.3.2.1
14.3.2.3	Box Plot of Change from Baseline in Pulse Rate (beats/min) Safety Population	IP	14.3.2.1
14.3.2.4	Box Plot of Change from Baseline in Respiration (breaths/min) Safety Population	IP	14.3.2.1
14.3.2.5	Box Plot of Change from Baseline in Weight (kg) Safety Population	IP	14.3.2.1
14.3.2.6	Box Plot of Change from Baseline in in Temperature (C) Safety Population	IP	14.3.2.1
14.4 Figure	Figure for PK and PD Data		
14.4.1	Box Plot of Neflamapimod Concentrations by Visit Safety Population	IP	
14.4.2.1.1	Scatter Plot: CTrough vs. Change from Baseline in CSF Biomarker (T-tau) Efficacy Population	IP	
14.4.2.1.2	Scatter Plot: CTrough vs. Change from Baseline in CSF Biomarker (P-tau181) Efficacy Population	IP	14.4.2.1.1
14.4.2.1.3	Scatter Plot: CTrough vs. Change from Baseline in CSF Biomarker (Aβ1-40) Efficacy Population	IP	14.4.2.1.1
14.4.2.1.4	Scatter Plot: CTrough vs. Change from Baseline in CSF Biomarker (Aβ1-42) Efficacy Population	IP	14.4.2.1.1
14.4.2.1.5	Scatter Plot: CTrough vs. Change from Baseline in CSF Biomarker (Neurofilament light chain) Efficacy Population	IP	14.4.2.1.1

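### The PK-outcome correlations are set on the two-arm Efficacy Population; if placebo subjects carry a concentration value, the coefficients would largely restate the arm difference instead of testing exposure-response.

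*SAP*

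**What the plan says.** **Population named for the correlations (SAP 11).** Table 14.4.2 is "Correlation Analysis of PK Parameters and Efficacy Data (Combined Change in Z-score, Change in WMS, CDR-SB) Efficacy Population" and Table 14.4.3 is "Correlation Analysis of PK Parameters and Change from Baseline in CSF Biomarkers Efficacy Population". The scatter plots, Figures 14.4.2.x and 14.4.3.x, follow suit, for example "Scatter Plot: CTrough vs. Change from Baseline in Clinical Dementia Rating Scale-Sum of Boxes (CDR-SB) Efficacy Population".

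**What that population is.** SAP 6.1.2 "includes all subjects who received at least one dose of study drug and had at least one post-dose efficacy assessment". SAP 6.1.1 makes clear that study drug means neflamapimod or placebo, so both arms are in it.

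**The alternative already defined.** The PK Population in SAP 6.1.4 is the randomized subjects who "received at least one dose of study drug in neflamapimod treatment group and had at least one post-dose PK data assessment". SAP 6.11 reports concentrations on it, and Tables 14.4.1.1 to 14.4.1.3.x use it. Figure 14.4.1 departs from this: "Box Plot of Neflamapimod Concentrations by Visit Safety Population".

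**Who is sampled.** Protocol 6.2.5 states that "PK profiles will be obtained in all subjects and correlated against CYP2C19 genotype", and Protocol 6.2.8 describes blood collection on Days 21, 42 and 84 without limiting it to one arm.

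**How a sample becomes a parameter.** SAP 6.12 takes CTrough and Cmax from the observed Day 21 values at nominal hours 0 and 2.5. SAP 6.2.9 says that for a result recorded as less than x, "a value of x will be taken for analysis purposes", with no exception for drug concentrations. Neither 6.11 nor 6.12 leaves placebo out of the correlations, adds a treatment term, or gives a separate rule for unquantifiable concentrations.

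**The concern.** There is one active dose, so only the variation in concentration among neflamapimod subjects can show whether higher exposure goes with a better outcome. If placebo subjects enter the same coefficient at or near one low value, the data form two clusters. The slope between the clusters is the treatment difference, whatever happens within the active arm.

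This matters because the programme gives weight to such correlations. Protocol 1.3 uses a Phase 2a regression of memory improvement on plasma level (r-squared 0.70, p=0.001) to argue that the improvement was due to drug. Protocol 3.2.1.1 uses PK-PD correlations in its dose rationale. A reader of Table 14.4.2 could therefore take a significant coefficient as a second line of evidence beside the primary comparison, when it would be largely the same comparison in another form.

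**Working it through.** **Inputs from the documents.** 76 per arm, and effect sizes of 0.46 and 0.53 (SAP 4); 1:1 allocation to one active dose (SAP 5); two-sided 5% tests (SAP 6.10).

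**Assumptions not in the documents.** All placebo samples are assayed and carry one numeric value x, equal to 5% of typical active exposure. Active concentrations are lognormal with a CV of 30%, 50% or 80%. The outcome has SD 1, arm difference d, and no relation to concentration within the active arm. All 76 per arm contribute. The SAP does not name the coefficient, so Pearson and Spearman were both examined.

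**Step 1: the plan's own power.** Normal approximation: power = Φ(d·√(76/2) − 1.960).
- d = 0.46: 0.46 × 6.164 = 2.836, and Φ(0.876) = 80.9% (noncentral t, 150 df: 80.4%).
- d = 0.53: 0.53 × 6.164 = 3.267, and Φ(1.307) = 90.4% (noncentral t: 90.1%).

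Both stated figures reproduce.

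**Step 2: what the pooled coefficient measures.** With equal arms, the correlation of outcome with a pure arm indicator is d/√(d² + 4). At d = 0.46 this is 0.46/√4.2116 = 0.224. With the active mean scaled to 1, concentration correlates with the arm indicator at 1/√(1 + 2CV²/(1 − x)²). With no exposure-response within the arm, the pooled correlation is the product of the two. For x = 0.05, (1 − x)² = 0.9025. The Fisher approximation to the chance of significance is Φ(√149·atanh(r) − 1.960).

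| CV | Factor | Pooled r at d = 0.46 | Chance of significance |
|---|---|---|---|
| 30% | 1/√1.199 = 0.913 | 0.205 | Φ(0.575) = 72% |
| 50% | 1/√1.554 = 0.802 | 0.180 | Φ(0.259) = 60% |
| 80% | 1/√2.418 = 0.643 | 0.144 | Φ(−0.189) = 43% |

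The pooled coefficient is the arm contrast, shrunk by the spread of active concentrations.

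**Step 3: simulation.** 10,000 trials per setting, x = 5% of the active median. Share of trials with p < 0.05:

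| d | Pooled Pearson, CV 30 / 50 / 80% | Pooled Spearman | Active arm only, Pearson |
|---|---|---|---|
| 0 | 4.8 / 4.9 / 4.7% | about 5% | 4.5-4.9% |
| 0.20 | 20.0 / 16.5 / 12.6% | 19-20% | 4.8-5.3% |
| 0.46 | 73.6 / 61.5 / 45.2% | 72% | 4.7-5.0% |
| 0.53 | 83.5 / 73.4 / 55.9% | 83% | 4.6-5.4% |

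Mean pooled Pearson r at d = 0.46 was 0.205, 0.182 and 0.148, in line with Step 2. Setting x at 5% of the active mean instead of the median gives 45-73% at d = 0.46.

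**Step 4: does the value given to placebo matter?** At d = 0.46 and CV 50%, pooled Pearson is significant in 62% of trials with placebo at 5% of the median, 63% with placebo at 0, and 57% with placebo at 20% of the median. The exact value makes little difference; pooling the arms is the cause.

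**The case against.** **Pooling is not spelled out, and some text points away from it.** SAP 6.3 gives PK and PD table shells treatment columns with no overall column. Under that layout a placebo column at one constant value would have no defined correlation. PK parameters are themselves tabulated on the neflamapimod-only PK Population, and Protocol 8.4 describes Day 21 concentrations for the neflamapimod group. Efficacy Population in the titles may mean only that the outcome must exist, with subjects who lack a PK parameter dropping out. This makes pooling less likely. It does not exclude it, because 6.3 governs summary columns and does not address the correlation step, and the population named includes placebo.

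**The harm needs facts that the documents do not give.** Sampling in all subjects does not show that placebo samples are assayed, or how unquantifiable results are recorded. If they are not assayed, placebo subjects have no PK parameter and only a wrong population label remains. This stands, and it makes the point conditional.

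**Nothing confirmatory depends on these results.** SAP 6.12 calls the correlations with HVLT-R, WMS and CDR exploratory, SAP 6.10.7 treats secondary and supportive results as descriptive, and no decision rule uses them. This stands too.

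**Three stronger readings are tempting, and the documents and figures do not support them.**
- A reader might infer that pooling produces false evidence of a drug effect. It does not: with d = 0 the pooled test rejects at about 5%.
- A reader might blame the less-than-x rule in SAP 6.2.9. Step 4 shows that coding placebo as 0 gives nearly the same result. The rule's only part is that it can turn a placebo result into a usable number.
- A reader might infer that Phase 3 dose choice would be misled. The trial has one active dose, and Protocol 1.3 ties Phase 3 design to treatment effects on the CDR, not to these tables.

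**Conclusion.** The point holds as a conditional fault in the stated analysis population. The titles of Tables 14.4.2 and 14.4.3 and of the scatter plots allow placebo subjects into a coefficient meant to describe exposure-response, and nothing in SAP 6.11 or 6.12 prevents it.

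If placebo samples carry values, an arm difference alone at the plan's 80%-power effect makes the pooled Pearson correlation significant in roughly half to three-quarters of trials. The same test in the active arm alone holds its nominal level. The Pearson range comes from the assumed CV of 30-80%; Spearman hardly depends on it. Fewer than 76 evaluable subjects per arm would lower the pooled percentages without changing the conclusion.

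The fault is one of interpretation: the coefficient would not be independent of the primary comparison. Separately, and with no assumption needed, the population named for Figure 14.4.1 conflicts with SAP 6.11.

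**What to change.** - **Tables 14.4.2 and 14.4.3:** compute the coefficients on neflamapimod subjects who are in both the PK Population and the Efficacy Population, and say so in the titles and in SAP 6.12.
- **Figures 14.4.2.x and 14.4.3.x:** draw them on the same subjects. If placebo subjects are shown for reference, mark them and leave them out of any coefficient or fitted line.
- **Figure 14.4.1:** change Safety Population to PK Population.

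No special coding rule for unquantifiable concentrations is needed for this point.

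**Cost.** SAP wording and population flags in the table and figure shells; no additional data. The coefficients would rest on at most 76 points instead of up to 152. The smallest Pearson r that reaches two-sided 5% rises from 1.976/√(150 + 1.976²) = 0.16 to 1.993/√(74 + 1.993²) = 0.23. That is the real precision available for exposure-response at one dose. The change is best made before unblinding, so that the choice of subjects cannot follow the results.
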